### **2.1.1.3 Day of last dose of study treatment**

The date of last dose will be collected via the CRF. The subject’s exposure will be calculated considering the end of study period visit (including follow-up visits F4, F8) or last dose day +84 days whichever occurs earlier.

## **2.2 Analysis sets**

The following analysis sets will be used for the data analysis. Rules of exclusion criteria of analysis are detailed in [Section 5.6](#).

The **Randomized Analysis Set (RAS)** consists of all randomized subjects. Subjects will be analyzed according to the treatment assigned at randomization.

The **Full Analysis Set (FAS)** comprises all subjects to whom study treatment has been assigned. Subjects will be analyzed according to the treatment assigned to at randomization. Mis-randomized subjects (mis-randomized in IRT) will be excluded from FAS. Mis-randomized subjects are defined as cases where IRT contacts were made by the site either prematurely or

inappropriately prior to confirmation of the subject's final randomization eligibility and no study medication was administered to the subject.

The **Safety Set** includes all subjects who received at least one dose of study treatment. Subjects will be analyzed according to the study treatment received, where treatment received is defined as the randomized/assigned treatment if the subject took at least one dose of that treatment or the first treatment received if the randomized/assigned treatment was never received.

The summary statistics analyses in this study will be performed according to domains with respective specifications of analyses sets, analyses period and treatment groups ([Table 2-1](#)).

**Table 2-1** Summary statistics specifications

Domains	Analyses sets	Analysis Period	Treatment group labels for each analysis period
Patient disposition, Demographics, Other baseline characteristics *	RAS	Treatment Period 1	Secukinumab 300 mg Q4W Placebo Total
		Treatment Period 2 Follow up (only for disposition tables)	Secukinumab 300 mg Q4W Secukinumab 300 mg Q2W Total
Efficacy endpoints	FAS	Treatment Period 1	Secukinumab 300 mg Q4W Placebo
		Entire treatment period	Secukinumab 300 mg Q4W Placebo Placebo-Secukinumab 300 mg Q2W
Safety data (Number of doses, duration of exposure, prior and concomitant therapies, concomitant medical procedures, significant non-drug therapies, laboratory data, AEs, etc.)	Safety set	Treatment Period 1	Secukinumab 300 mg Q4W Placebo
		Entire treatment period	Secukinumab 300 mg Q4W Secukinumab 300 mg Q2W Placebo Any Secukinumab

\* Treatment groups for protocol deviations for entire treatment period: AIN457 300 mg Q4W, AIN457 300 mg Q2W, Any AIN457 300 mg, Placebo, Total

## 2.2.1 Subgroup of interest

The efficacy endpoints will be evaluated by subgroups in an RShiny app. Subgroups of interest may include gender, age, Hepatitis C infection, weight, smoking history, previous systematics therapy for lichen planus, time since diagnosis, baseline IGA score and oral/genital affection in MLP.

## 2.3 Patient disposition, demographics and other baseline characteristics

The analyses of patient disposition, demographics and other baseline characteristics will be based on the randomized set.

Summary analyses in this section 2.3 will be shown by treatment groups as specified in [Table 2-1](#).

### 2.3.1 Patient disposition

The number of subjects screened will be presented. In addition, the reasons for screen failures will be provided. The number and percentage of subjects in the randomized set who completed Treatment Period 1, Treatment Period 2 and Follow up Period, and who discontinued the study prematurely (including the reason for discontinuation) will be presented by study period for each treatment group.

For each protocol deviation, the number and percentage of subjects for whom the deviation applies will be tabulated by treatment group.

### 2.3.2 Demographics and other baseline characteristics

Common background and demographic variables will be analyzed in the randomized set.

For three lichen planus subtype cohorts (predominant subtype), summary statistics for these variables will be analyzed for each cohort ([Section 2.1](#)) and for each treatment group ([Table 2-1](#)) according to the type of variables as continuous or discrete. Summary statistics could be analyzed across three cohorts.

Lichen planus specific baseline characteristics and history of disease will be summarized for three cohorts (predominant subtypes) as follows.

**Table 2-2 Demographics and other baseline characteristics**

Variable(s)	Cohorts applied
Demographics	
Continuous	
Age	
Height	
Weight	
Body mass index (BMI)	
Categorical	
Age categories (<65 years, 65 years and older)	CLP, MLP, LPP, All

Variable(s)	Cohorts applied
Gender	
Race	
Ethnicity	
Smoking status at baseline	
Lichen planus specific baseline characteristics	
Continuous	
Patient Assessment of Itch (by each of the three questions)	CLP, MLP, LPP, All
Patient Assessment of Pain (by each of the three questions)	
Dermatology Life Quality Index (DLQI)	
Time since diagnosis of predominant lichen planus	
Reticular Erythematous Ulcerative score (REU)	MLP
Oral Lichen Planus Symptom Severity Measure (OLPSSM)	MLP
Lichen Planopilaris Activity Index (LPPAI)	LPP
Scalpdex	LPP
Categorical	
IGA score (at least moderate and severe)	CLP, MLP, LPP, All
Hepatitis C infection	
Previous exposure to biological systemic medication for lichen planus (yes, no)	
Previous exposure to non-biologic systemic medication for lichen planus (yes, no)	
Current use of topical medications (excluding ultrahigh or high potency corticosteroids, as per WHO classification) (yes, no)	
Percentage of patients with concomitant MLP	CLP
Baseline IGA score of concomitant MLP (at least mild, moderate, and severe)	CLP
Anatomical location of concomitant MLP (Oral, Genital, Esophageal)	CLP, MLP, All
Percentage of patients with concomitant CLP	MLP
Baseline IGA score of concomitant CLP (at least mild, moderate, and severe)	MLP

*Body Mass Index (BMI)* will be calculated using the following formula:

$$\text{BMI} = (\text{body weight in kilograms}) / (\text{height in meters})^2$$

For BMI, height and body weight of the last value prior to first dose will be used as a baseline value. If there is no weight or height recorded prior to taking the study treatment, BMI will be missing.

Time since diagnosis of the lichen planus (predominant subtypes) will be calculated using the following formula:

- Time since diagnosis of predominant lichen planus= (inform consent date – diagnosis date of the predominant lichen planus (from medical history CRF page) + 1)/365.25

Any condition entered on the relevant medical history / current medical conditions CRF will be coded using the MedDRA dictionary. They will be summarized by System Organ Class (SOC) and Preferred Term (PT) of the MedDRA dictionary.

## **2.4 Treatments (study treatment and concomitant medications)**

The analysis of study treatment data will be based on the safety set.

### **2.4.1 Study treatment / compliance**

The number of secukinumab and placebo injections doses will be summarized for Treatment Period 1 and entire treatment period by treatment group using contingency tables as specified in [Table 2-1](#).

The duration of exposure to study treatment will be summarized as the number of subjects with exposure of at least certain time thresholds, displayed using the following categories: “any exposure”, “≥1 week”, “≥2 week”, “≥3 week”, “≥4 weeks”, “≥8 weeks”, “≥12 weeks”, “≥16 weeks”, “≥24 weeks”, “≥32 weeks. The results will be presented by analyses periods and treatment groups as specified in [Table 2-1](#).

Duration of exposure will be defined as the time from first dose of study medication to the last dose plus 84 days or last visit (including follow-up visits) whichever occurs earlier. For subjects who discontinued or have their last visit earlier than last dose plus 84 days, the end of study treatment exposure will be the date of the last study visit in the follow-up period or in the corresponding treatment period.

Duration of exposure (days) = min (“end of study” date, last dose date +84) – first dose date +1

Duration of exposure (years) = duration of exposure (days) / 365.25

### **2.4.2 Visit windows**

*Visit windows* will be used for the data that is summarized by visit; they are based on the study evaluation schedule and comprise a set of days around the nominal visit day. For any assessment, there are protocol defined scheduled visits around which visit windows were created to cover the complete range of days within the study. For subjects randomized to Placebo group to secukinumab 300 mg every 2 weeks arm, the day of taking the first secukinumab dose will also need to be taken into visit window consideration. The visit windows are shown in [Table 2-3](#). In this table, the days are counted since the first dose of study treatment (study days) for safety assessments and the days are counted since the date of randomization for efficacy assessments. These visit windows apply to measurements taken at every visit. For assessments collected less often different visit windows will be applied as detailed below.

When visit windows are used, all visits will be re-aligned, i.e. they will be mapped into one of the visit windows. E.g., if the Week 4 visit of a subject is delayed and occurs on Day 60 instead of on Day 29, it will be re-aligned to visit window Week 8. In the case of major deviations from the visit schedule, or due to unscheduled visits, several assessments of a subject may fall in a particular visit window (either scheduled or unscheduled). Statistical approaches to handle multiple assessments in a given visit window are specified in [Section 2.4.3](#).

**Table 2-3      Assessment windows for scheduled visits**

Analysis Visit	Week	Scheduled Day	Visit Window
Baseline	BSL	1	-28 days to Day 1*
Week 2	2	15	Day 2-22
Week 4	4	29	Day 23-43
Week 8	8	57	Day 44-71
Week 12	12	85	Day 72-99
Week 16	16	113	Day 100-127
Week 20	20	141	Day 128-155
Week 24	24	169	Day 156-183
Week 28	28	197	Day 184-211
Week 32	32	225	Day 212-239
Week 36	36	253	Day 240-267
Week 40	40	281	Day 268-295

\* Day 1 is the date of the first drug administration for safety assessments and the date of the randomization for efficacy assessments.

For parameters which are not collected at every visit (e.g. laboratory, Lichen Planopilaris Activity Index), visit windows defined in Table 2-3 will be combined. The following rules are used to determine the visit window for an applicable visit post baseline: “Lower limit” = “upper limit of prior applicable visit” + 1. “Upper limit” = “target day of current visit” + integer part of (“target day of next applicable visit” – “target day of current visit”)/2. For example, if a parameter is measured at Week 12 and Week 28 only, Week 12 visit window will extend from Day 2 to Day 141 (combining Week 1 to Week 20 visit windows), Week 28 will extend from Day 142 to Day 295 (combining Week 21 to Week 40). If more than one assessment falls into the interval, the rules defined in Section 2.4.3 below are applied.

The analysis visit will be used for listing of visit and period for both safety and efficacy data. If a visit falls after the last visit window (after Day 295) it is not assigned an analysis visit and will be listed under label “After Week 40”.

#### **2.4.3      Multiple assessments within visit windows**

When there are *multiple assessments* in a particular visit window, the following rules are applied to select one value “representing” the subject in summary statistics in a visit window (Table 2-4).

For baseline assessment definition, see [Section 2.1.1.2](#). For post-baseline visit windows the

following applies (unless otherwise specified):

- for *quantitative variables*, the *closest* to the actual visit is chosen (if two assessments have the same distance, then the earlier one will be chosen);
- in case qualitative variables are based on quantitative variables, the visit will be assigned to the quantitative variable, and this visit will be used for the derived qualitative variable.

**Table 2-4 Rules for selecting values for analysis within a given visit window**

Timing of measurement	Type of data	Rule
Baseline	All data	See Section 2.1.1.2
Post-baseline efficacy	All data except for PRO (e.g., IGA)	The measurement closest to the target day will be used. In the event two measurements are taken equally apart (e.g., 1 day before target date and 1 day after), the results from the earlier visit will be used. If two measurements are taken on the same day, then select the first one using eCRF visit number. If two measurements have been taken on the same day and same visit then select the worst.
	PRO data	The measurement closest to the target day will be used. In the event two measurements are taken equally apart (e.g., 1 day before target date and 1 day after), the earlier one will be used. If two measurements have been taken on the same day, select the worst. If two measurement have the same value, select the first one using eCRF visit number.
Post-baseline safety	Summary information (e.g. laboratory values, vital signs, etc.)	The (non-missing) measurement closest to the target day will be used. In the event two measurements are taken equally apart (e.g. 1 day before target date and 1 day after) the first one will be used. If two measurements are taken on the same day then select the first one (using the time). If two measurements are taken on the same date/time then use the first visit number (assuming this is the planned visit). If two measurements are taken on the same date/time/eCRF visit number then use the average of two assessments.
Post-baseline safety	Notable abnormalities for laboratory values	The most extreme measurement in the window will be used. Note this means a subject can have a notably high and notably low measurement within an analysis period.

#### **2.4.4 Prior, concomitant and post therapies**

Medications will be identified using Novartis Drug and Therapy Dictionary (NovDTD) including Anatomical Therapeutic Chemical (ATC) code. Prior and concomitant treatments will be summarized by Treatment Period 1 and entire treatment period and by respective treatment groups (Table 2-1).

Prior medications are defined as drugs taken and stopped prior to the first dose of study treatment. Any medication given at least once between the day of first dose of study treatment, and within 84 days after last dose will be a concomitant medication, including those that were started before first dose of study treatment and continued into the Treatment Period.

Prior or concomitant medication will be identified based on recorded or imputed start and end dates of medication taken (see [Section 5.1.3](#)).

Medications will be presented in alphabetical order, by ATC codes and grouped by anatomical main group (the 1st level of the ATC codes). Tables will also show the overall number and percentage of subjects receiving at least one drug of a particular ATC code and at least one drug in a particular anatomical main group.

In addition, medical procedures and significant non-drug therapies as coded in MedDRA will be summarized.

## **2.5 Analysis of the primary objective**

The primary aim of the study is to demonstrate the efficacy of secukinumab (300 mg Q4W) with respect to IGA responder status after 16 weeks of treatment compared to placebo.

### **2.5.1 Primary endpoint**

The primary endpoint of the study is the proportion of IGA responders within each cohort at Week 16, where IGA response is defined as achieving an absolute IGA score less than or equal to 2. Each cohort (CLP, MLP and LPP) of the study will have its own primary efficacy endpoint analyzed separately.

The analysis of the primary endpoint will be based on the FAS.

### **2.5.2 Statistical hypothesis, model, and method of analysis**

The primary endpoint of IGA response at Week 16 is a binary (yes/no) outcome; it will be analyzed by a Bayesian method based on the Beta-Binomial model. Bayesian inference based on the non-informative prior of Beta (1/3, 1/3) for each treatment group will be used to obtain the posterior distribution of the treatment difference between secukinumab and placebo for the three subtypes, respectively.

The Bayes PoC criteria to be assessed for the primary endpoint are:

1) the posterior probability of the treatment difference greater than zero ( $\delta > 0$ ) is greater than 90%;

$$\Pr(\delta \text{ (secukinumab, placebo)} > 0 \mid \text{data}) > 90\% \text{ and}$$

2) the posterior probability of the treatment difference exceeding half of the target effect of 0.30 ( $\delta > 0.15$ ) is greater than 50%

$$\Pr(\delta \text{ (secukinumab, placebo)} > 0.15 \mid \text{data}) > 50\%$$

where  $\delta$  denotes the treatment difference between secukinumab and placebo with respect to the

IGA response at Week 16.

### **Bayesian model**

The statistical model used will include a fixed factor for treatment (secukinumab or placebo). It is assumed that the number of responder patients is a random variable following a binomial distribution Binomial ( $n_k, p_k$ ) where  $n_k$  is the sample size and  $p_k$  is the true underlying proportion of responder patients. Given the prior of Beta (1/3, 1/3) for each treatment group, the posterior of  $p_k$  is also a Beta distribution as following:

$$p_k | s_k \sim \text{Beta}(1/3 + s_k, 1/3 + n_k - s_k)$$

where  $s_k$  is the observed number of patients who have responded among the  $n_k$  patients observed.

Estimates of the posterior probabilities of the difference of the IGA responder rate between the secukinumab 300 mg treatment and placebo groups at Week 16 will be presented together with two sided 95% credible intervals (2.5% to 97.5%). Estimates of the posterior probabilities of the efficacy criteria (criteria 1 and 2) being met will be provided.

The posterior beta density function of the estimated proportion of responders will be displayed graphically.

#### **2.5.3 Handling of missing values/censoring/discontinuations.**

Subjects who discontinue treatment before Week 16 will be considered failures (i.e., non-responder). Missing values not related to treatment discontinuation will be analyzed as observed.

#### **2.5.4 Supplementary analyses**

Two supplementary analyses are planned.

##### **2.5.4.1 Hypothetical strategy**

A supplementary analysis will evaluate the treatment effect assuming that patients would not discontinue study drug for the intended duration of 16 weeks (hypothetical strategy). Data after study treatment discontinuation will be replaced by multiple imputed data using the MAR (missing at random) assumption. Detail information could be found in the Estimand charter (Section 5.4 and Section 5.5.2).

## 2.6 Analysis of secondary objectives

### 2.6.1 Secondary endpoints

Secondary efficacy endpoints will be analyzed separately for each independent cohort (CLP, MLP, LPP) or for one specific cohort, as specified in [Table 2-5](#). Treatment groups for summary statistics are summarized in [Table 2-1](#).

- Endpoints for each independent cohort

#### Investigator's Global Assessment (IGA)

The following IGA related endpoints are considered:

- **IGA  $\geq 2$  points improvement response:** defined as achieving an  $\geq 2$  IGA score decreasing compared with baseline (thus at least achieving an IGA score of  $\leq 2$ ).
- **IGA 0 or 1 response:** defined as achieving an IGA score of 0 or 1 (thus at least achieving an IGA  $\geq 2$  points improvement)

For IGA  $\geq 2$  points improvement response and IGA 0 or 1 response from Week 1 to Week 16, comparisons between the 300 mg Q4W treatment regimen and placebo groups will be conducted using the Fisher exact test. Estimates of the difference of response rates between the 300 mg Q4W treatment regimen and placebo groups together with 95% confidence intervals will be presented.

Summary statistics for IGA  $\geq 2$  points improvement and IGA 0 or 1 response by visit from baseline up to the end of study for each treatment group will be presented in contingency tables with the number and percentage of subjects in each category.

### **Dermatology Life Quality Index**

Seven scores will be derived from the DLQI: the total score of each of the six dimensions and the total score over all items. The higher the score, the more quality of life is impaired. The DLQI total score over all items will be calculated by summing the score of each question resulting in a maximum score of 30 and a minimum score of 0.

For the total DLQI score and each of the seven total item scores, summary statistics will be provided for the absolute and percentage change from baseline by visit up to the end of study for each treatment group.

Achievement of DLQI total score of 0 or 1 among subjects with baseline DLQI score  $\geq 2$  will be considered as a DLQI 0/1 responder. The number and proportion (%) of DLQI responders will be presented by visit up to the end of study for each treatment group. Between-treatment differences for the proportion of DLQI responder from Week 1 to Week 16 together with 95% confidence intervals will be presented.

### **Patient Assessment of Itch (NRS)**

Itch is assessed with three questions about an overall severity, severity at the worst moment and the overall degree of bother, respectively. Each of the question will be answered using a numeric rating scale (NRS, ranging from 0 to 10).

For each of the three questions, summary statistics will be provided for the absolute and percentage change from baseline by visit up to the end of study for each treatment group.

### **Patient Assessment of Pain (NRS)**

Pain is assessed with three questions, each answered using a numeric rating scale (NRS, ranging from 0-10).

For each of the three questions, summary statistics will be provided for the absolute and percentage change from baseline by visit up to end of study for each treatment group.

- Endpoint for CLP**

### **Physician Assessment of Surface Area of Disease (PSAD) for Skin Disease**

PSAD evaluates the extent of cutaneous lesions. PSAD ranges from 0 to 5, with lower scores corresponding to lower percentages of surface area with disease.

The number and percentage of subjects in each category will be presented by visit up to the end of study for each treatment group.

- Endpoints for MLP**

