

• Patient assessment of pain (NRS)

	

• Absolute and relative change in NRS from baseline to Week 16 and 32, and throughout the duration of the study

• To assess the safety and tolerability of secukinumab in subjects with lichen planus.

	

• Adverse events, laboratory values, vital signs

Cutaneous Lichen Planus (CLP)	

• Physician Assessment of Surface Area of Disease (PSAD) for Skin Disease

	

• Absolute and relative change in PSAD from baseline to Week 16 and 32, and throughout the duration of the study

Mucosal Lichen Planus (MLP)	

• Reticular Erythematous Ulcerative (REU) score

• Oral Lichen Planus Symptoms Severity Measure (OLPSSM) score

	

• Absolute and relative change in REU score from baseline to Week 16 and 32, and throughout the duration of the study

• Absolute and relative change in OLPSSM score from baseline to week 16 and 32, and throughout the duration of the study

Lichen Planopilaris (LPP)	

• LPP Activity Index (LPPAI)

• SCALPDEX Questionnaire

	

• Absolute and relative change in LPPAI score from baseline to Week 16 and 32, and throughout the duration of the study

• Absolute and relative change in SCALPDEX Questionnaire score from baseline to Week 16 and 32, and throughout the duration of the study

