### **Physician Assessment of Surface Area of Disease (PSAD) for Skin Disease**

The number and percentage of subjects in each category will be presented by visit up to the end of study for each treatment group.

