

• Patient assessment of pain (NRS)

	

• Absolute and relative change in NRS from baseline to Week 16 and 32, and throughout the duration of the study

• To assess the safety and tolerability of secukinumab in subjects with lichen planus.

	

• Adverse events, laboratory values, vital signs

Cutaneous Lichen Planus (CLP)	

• Physician Assessment of Surface Area of Disease (PSAD) for Skin Disease

	

• Absolute and relative frequencies in PSAD from baseline to Week 16 and 32, and throughout the duration of the study

Mucosal Lichen Planus (MLP)	

• Reticular Erythematous Ulcerative (REU) score

	

• Absolute and relative change in REU score from baseline to Week 16 and 32, and throughout the duration of the study

• Oral Lichen Planus Symptoms Severity Measure (OLPSSM) score

	

• Absolute and relative change in OLPSSM score from baseline to week 16 and 32, and throughout the duration of the study

Lichen Planopilaris (LPP)	

• LPP Activity Index (LPPAI)

	

• Absolute and relative change in LPPAI score from baseline to Week 16 and 32, and throughout the duration of the study

• SCALPDEX Questionnaire

	

• Absolute and relative change in SCALPDEX Questionnaire score from baseline to Week 16 and 32, and throughout the duration of the study

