### **Reticular erythematous Ulcerative (REU) score**

The REU score was developed as a semi-quantitative scale, measuring disease severity based on 3 dimensions: reticulation, erythema and ulceration. Scores for each of the 3 clinical dimensions will add up to a total weighted score (REU score).

Summary statistics for the REU score will be provided for absolute and percentage change from baseline by visit up to end of study for each treatment group.

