**Table 2-5 Overview of analysis methods for secondary efficacy variables**

Variable(s)	Cohorts applied	Summary statistics for discrete data	Statistical analyses	Summary statistics for continuous data	Graphs*
IGA response over time a	CLP, MLP, LPP	X	Fisher exact test @ Week 1- 16		X
DLQI 0/1 response over time	CLP, MLP, LPP	X			X
DLQI total score and item score overtime	CLP, MLP, LPP			X	X b
Patient Assessment of Itch (NRS) over time (3 questions)	CLP, MLP, LPP			X	
Patient Assessment of Pain (NRS) over time (3 questions)	CLP, MLP, LPP			X	
PSAD over time	CLP	X			X c
REU over time	MLP			X	X d
OLPSSM over time	MLP			X	
LPPAI responder and partial responder over time	LPP	X			
LPPAI score over time	LPP			X	X d
Scalpdex over time	LPP			X	

\*Line plots. The graphs may only be presented in the Rshiny app where appropriate.

aIGA responses include: 1) IGA ≥2 points improvement response and 2) IGA= 0 or 1 response.

bTotal DLQI score change from baseline by cohort.

cPlotted as a categorical variable.

dTime course of percent change from baseline.

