## 2.6.3 Handling of missing values/censoring/discontinuations

Data collected after treatment discontinuation by Week 32 will be replaced with the baseline value of the patients for all secondary endpoints above. Missing values not related to treatment discontinuation will be analyzed as observed.

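### The listed CLP endpoint is change in PSAD from baseline, but the visible plan reports only category counts per visit, which do not show how many patients improved or worsened, or by how much.

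*SAP*

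**What the plan says.** Protocol Table 2-1 has one entry under the CLP heading: "Absolute and relative change in PSAD from baseline to Week 16 and 32, and throughout the duration of the study".

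Protocol 12.5.1 gives the planned PSAD analysis as "The number and percentage of subjects in each category will be presented by visit", up to the end of the study and by treatment group. SAP 2.6.1 carries the same sentence: "The number and percentage of subjects in each category will be presented by visit up to the end of study for each treatment group". SAP Table 1-1 restates the endpoint as "Absolute and relative frequencies in PSAD from baseline to Week 16 and 32". SAP Table 2-5 marks PSAD for discrete summaries only, with a graph footnoted "Plotted as a categorical variable".

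On the scale itself, SAP 2.6.1 says "PSAD ranges from 0 to 5, with lower scores corresponding to lower percentages of surface area with disease", which makes six ordered grades.

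The other secondary scores are treated differently. For REU, in the mucosal cohort, "Summary statistics for the REU score will be provided for absolute and percentage change from baseline by visit". DLQI, itch, pain, OLPSSM, LPPAI and Scalpdex also get absolute and percentage change. SAP Table 2-2 lists baseline REU, OLPSSM, LPPAI and Scalpdex, but not PSAD.

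**The concern.** An endpoint defined as change from baseline is a property of each patient: a baseline grade paired with a later grade. A table of how many patients sit in each grade at each visit breaks that pairing. The visible text of either document derives no PSAD change score, shift table or improved/worsened count, and no reason is given for treating PSAD differently from the other secondary scores.

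What is at stake is how well the CLP cohort can be described. Protocol 8.3.5 calls PSAD unvalidated and says this study should clarify its role in judging severity. Whether a scale responds to treatment is judged mainly from within-patient movement. With 24 and 12 patients per arm, a chance difference in baseline extent also carries into the Week 16 counts. A reader would have to allow for it by eye.

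**Working it through.** The documents give no figure for PSAD, so there is none to reproduce. The 71% proof-of-concept probability (0.712 in Protocol Table 12-1) does reproduce, but it concerns IGA response and does not enter here.

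**Inputs.** Six grades, 0 to 5 (SAP 2.6.1). Arms of 24 and 12 (Protocol 12.8). The category counts below are assumed for illustration, for 24 patients all seen at both visits.

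**Formulas.** Let B(k) and W(k) be the numbers at grade k or lower at baseline and Week 16, with B(-1) = W(-1) = 0 and n = 24. Lower is better.

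- Fewest improved = the larger of 0 and max over k of [W(k) - B(k)]
- Most improved = n - max over k of [B(k) - W(k-1)]
- Fewest worsened = the larger of 0 and max over k of [B(k) - W(k)]
- Most worsened = n - max over k of [W(k) - B(k-1)]

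**Case 2 worked through.** Baseline 0/2/6/8/6/2 gives B = 0, 2, 8, 16, 22, 24. Week 16 counts 0/4/8/6/4/2 give W = 0, 4, 12, 18, 22, 24.

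- W(k) - B(k) = 0, 2, 4, 2, 0, 0, so at least 4 improved and the minimum worsened is 0.
- B(k) - W(k-1) = 0, 2, 4, 4, 4, 2, so at most 24 - 4 = 20 improved.
- W(k) - B(k-1) = 0, 4, 10, 10, 6, 2, so at most 24 - 10 = 14 worsened.

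| Case | Baseline counts, grades 0-5 | Week 16 counts | Improved | Worsened |
|---|---|---|---|---|
| 1 | 0/2/6/8/6/2 | 0/2/6/8/6/2 | 0 to 16 | 0 to 16 |
| 2 | 0/2/6/8/6/2 | 0/4/8/6/4/2 | 4 to 20 | 0 to 14 |
| 3 | 0/2/6/8/6/2 | 2/6/8/6/2/0 | 8 to 24 | 0 to 10 |
| 4 | 0/0/8/8/8/0 | 8/16/0/0/0/0 | 24 | 0 |

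Linear programming over all possible baseline-by-Week-16 tables gives the same bounds.

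**What counts do show.** A downward shift in the same patients proves that some improved: at least 4, 8 and 24 in cases 2 to 4. If the grades are treated as equally spaced, the mean shift can also be recovered. In case 2 the mean grade goes from 72/24 = 3.00 to 64/24 = 2.67, a change of -0.33. The spread of individual changes, the number moving each way and the relative change cannot be recovered.

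**When even the lower bound fails.** It needs the same patients at both visits. SAP 2.6.3 analyses missing values unrelated to treatment discontinuation as observed, so the denominator can differ between visits. The same section says "Data collected after treatment discontinuation by Week 32 will be replaced with the baseline value of the patients for all secondary endpoints above". In a count table a substituted value looks like any observed grade; in a shift table it falls on the no-change diagonal.

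**Cell sizes in the placebo arm.** Counts by grade: 12/6 = 2 per cell on average. Improved/unchanged/worsened: 12/3 = 4. Full 6 by 6 shift table: 12/36 = 0.33.

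**The case against.** The strongest reply has five parts.

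- **The counts are informative.** A reader might infer that they cannot show any improvement at all. The working rules that out: a downward shift in the same patients shows some improved. This part stands, and the point is limited to how many and by how much.
- **The SAP did not override the protocol.** Setting Protocol Table 2-1 against SAP Table 1-1 invites that reading. But the SAP introduction says data are analysed according to protocol Section 12, and SAP 2.6.1 repeats Protocol 12.5.1. The conflict starts inside the protocol. This stands, and it means correcting the SAP alone would leave the protocol inconsistent.
- **Frequencies suit an ordinal grade with unequal bands.** This stands as a reason to keep the counts and to doubt percent change. It is no reason to leave out the direction of change. REU and LPPAI are composite scores, so treating them differently is not an error in itself.
- **A baseline imbalance would be visible.** Baseline is an analysis visit in SAP Table 2-3 and PSAD is scheduled then, so a by-visit table should carry a baseline row. This largely stands. Adding PSAD to Table 2-2 is a matter of completeness.
- **Little depends on PSAD.** The proof-of-concept rule uses IGA alone, and SAP Table 2-5 gives PSAD no test. The CLP column of the IGA also touches on extent, and itch, pain and DLQI are summarised for the cohort. This stands on importance. It does not supply the missing endpoint, because IGA grading is driven mainly by lesion characteristics while PSAD measures extent.

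**Conclusion.** The concern holds in a limited form. Following the visible text exactly would not report the within-patient change that Protocol Table 2-1 names as the only endpoint under the CLP heading. Depending on the counts, the planned table can leave the number improved almost open (0 to 16 of 24) or fix it completely (24 of 24). Those ranges rest on assumed counts and on the same patients at both visits.

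A reader might go further and say the endpoint is never computed. The documents do not support that: many SAP contents entries, and parts of its change history, are blacked out and could hold further PSAD analyses. Nor is the CLP efficacy conclusion at risk. The sample size, the primary analysis and the decision rule are untouched. This is a reporting gap in one descriptive secondary endpoint, worth closing because closing it is cheap.

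**What to change.** In SAP 2.6.1, Table 1-1 and Table 2-5, keep the category counts and add, by arm and visit, the number and percentage of CLP patients who improved by at least one category, were unchanged, or worsened relative to baseline. Add shift tables of baseline by Week 16 and baseline by Week 32. List baseline PSAD for CLP in Table 2-2.

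Align Protocol Table 2-1 and Protocol 12.5.1 with this. If percent change is dropped because PSAD is a 0-5 ordinal grade, record that as a deliberate change to the Table 2-1 endpoint, with the reason, since that table names relative change.

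The cost is one derived variable and a few tables from data already collected, with no effect on conduct. The drawback is sparse cells in the shift tables for the 12-patient placebo arm, so the improved/unchanged/worsened counts should carry the message.
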